9.1 Named authors

Named authors will be required to meet the International Committee of Medical Journal Editors (ICMJE) criteria (www.icmje.org) for authorship based on the following four criteria:

1. Substantial contribution to the conception or design of the work; or the acquisition, analysis or interpretation of the data for the work and

2. Drafting the work or revising it critically for important intellectual content and

3. Final approval of the version to be published and

4. Agreement to be accountable for all aspects of the work in ensuring that questions related to the accuracy or integrity of any part of the work are appropriately investigated and resolved.

The ICMJE states 'when submitting a manuscript authored by a group, the corresponding author should specify the group name if one exists and clearly identify the group members who can take credit and responsibility for the work as authors. The byline of the article identifies who is directly responsible for the manuscript and MEDLINE lists authors whichever names appear on the byline. If the byline includes a group name, MEDLINE will list the names of individual group members who are authors or who are collaborators, sometimes called non-author contributors, if there is a note associated with the byline clearly stating that the individual names are elsewhere in the paper and whether those names are authors or collaborators.'

All citable collaborators will therefore be listed at the end of the paper and their roles identified.

9.2 Citable collaborators

Citable collaborators will have made a considerable contribution to the study, but will not have met the ICMJE criteria for authorship (non-author contributors). These will include trainee or consultant leads at each centre and other trainees or team members (including consultant surgeons or oncologists, clinical nurse specialists or research nurses) who have recruited at least 5 patients to the study. Recruitment in this context includes the submission of at least five completed data sets. Judgement may be used to determine participation according to local centre practice. Unit leads will be asked to provide details of their local

team and whether individuals fulfil the criteria for citable or acknowledged collaborator status.

9.3 Acknowledged collaborators

Acknowledged collaborators will include consultant surgeons or oncologists who contributed patients to the study, but did not personally collect data or recruit patients and trainees who have made a lesser contribution to patient recruitment and data collection than that required for citable collaborator status. Trainees who are acknowledged contributors will also receive a certificate of participation for inclusion in their portfolios.

The final reports will be prepared in accordance with the STROBE(19) (Strengthening the Reporting of Observational Studies in Epidemiology) guidelines.

10. Research Governance

This is a prospective observational multicentre longitudinal cohort study to evaluate potential variation in treatment for patients diagnosed with LRR +/- DM. The patient's clinical care and management will not be affected by participating in the study given its non-randomised nature. Given the relatively small number of patients diagnosed with LRR in each UK breast unit, a national approach is required to examine current practice and examine long term oncological outcome in order to set national guideline and optimally manage this group of patients. Patients who consent to the study will give permission for their original and current cancer treatment details and outcome to be examined for research purpose. Patients will be free to withdraw their consent for the study at any time. In this circumstance, data up until the point of withdrawal will be used unless patients request removal of their data from the study database.

The feasibility of the recruitment process will be evaluated by using the screening logs, eligibility and consent processes. If reasons for ineligibility and non-participation have been provided, these will be summarised. Follow up retention, including the number of participants who withdraw and any reasons for withdrawal will be described.

There is no pre-defined safety end-point for this study. However, any adverse events which occur as a result of normal care will be reported to the study team. The study has been designed to avoid burden to the patient such as a need for extra hospital visits. This also

35

IRAS ID: 285389

The MARECA study Protocol version 4.0 25/05/2022
applies to the patients who consent for future access to tissue samples or slides. The stored tissue samples or slides will form part of routine clinical practice in the pathology laboratory (i.e. archival storage of FFPE tumour blocks as opposed to collection of fresh tissue that requires different storage technique with additional associated costs) and patients will not be asked to undergo any extra procedures for tissue sample access.

10.1 Ethical approval

Research Ethics Committee approval will be obtained for all sites registered for the study. The Investigator will submit and, where necessary, obtain approval from the above parties for any substantial amendments to the original approved documents. Patient consent will permit linkage of pseudonymised trial data to the hospital electronic records from the participating NHS Trusts. This will enable determination of oncological outcome of the study cohort at 3 and 5 years follow up time points.

10.2 Informed consent

The participant must personally sign and date the latest approved version of the Informed Consent form before any study specific procedures are performed. It is the responsibility of the Principal Investigator (or designee as listed on the Site Responsibilities Form) to obtain written informed consent in compliance with national requirements from each patient prior to entry into the study. Consent can be taken during normal clinic appointments or on the day of surgery, if applicable. If the patient wishes to participate, written informed consent will be taken by the Principal Investigator, a trainee lead or an appropriately trained member of the team (as previously mentioned). Patients will be reminded that participation is voluntary and that they can withdraw at any time point without this affecting their care. This process will be clearly documented in the patients' medical notes. A copy of the signed Informed Consent will be given to the participant. The original signed form will be retained in the trial site file and a copy will be placed in the patient's notes. Consent will be sought specifically to determine oncological outcome of the study cohort with optional consent to donate archived tissue samples or slides for a future translational study. Patients will also be free to withdraw from the study at any time. Any data acquired prior to withdrawal will be included in the final analysis (unless consent is withdrawn by the participant). The reason for withdrawal will be recorded.

10.3 Study reporting

The CI shall submit once a year throughout the study, or on request, an Annual Progress Report to the REC, host organisation and Sponsor. In addition, an End of Trial notification and final report will be submitted to the REC, host organisation and Sponsor.

10.4 Patient confidentiality

The study staff will ensure that the participants' anonymity is maintained. The participants will be identified only by participants ID number on the CRF and any electronic database. All documents will be stored securely and only accessible by authorised personnel. The trial will comply with the Data Protection Act, which requires data to be anonymised as soon as it is practical to do so.

10.5 Archiving

In line with the principles of GCP/UK Clinical trial Regulations guidelines, at the end of the study, data will be securely archived at the centre for a minimum of 25 years. Arrangements for confidential destruction will then be made. If a patient withdraws consent for their data to be used, it will be confidentially destroyed immediately. No records may be destroyed without first obtaining written permission from the Sponsor.

10.6 Insurance

NHS indemnity through the Clinical Negligence Scheme for Trusts (CNST).

11. Public and Patient Involvement

MARECA study has been designed to collect and analyse information about tumour characteristics and treatment details for the patient's original and recurrent breast cancer. The study goal is to improve understanding of how this group of patients are currently being treated in the UK, as well as identify any variations in treatment. Following the patient's long term treatment outcome will enable the research team to study tumour characteristics and treatment details in order to identify patient groups where treatment outcome was suboptimal. This will in turn enable future research and treatments to be targeted and tailored in order to improve future patient outcome. Cancer recurrence and long term outcomes of treatment were key themes that emerged from the National Cancer Research Institute's 'living with and beyond cancer research priorities' project[69], who surveyed over 3500 patients, carers, and health and social care professionals.

We have gained valuable input from a patient representative group (Independent Cancer Patients' Voice, ICPV) in setting up the MARECA study, especially in drafting the patient information sheet and the patient consent form, which are concise and easy to understand from the patient and family member's point of view. We have ensured that these documents contain appropriate wording and phrases for patients eligible to join the study. This is especially important given the impact of cancer recurrence diagnosis to the patient and family members. We have also received positive feedback on the phrasing of the patient information sheet from the 'Pink Events', a breast cancer charity comprised of committee members who have been treated for breast cancer in the past.

12. Study Management

Oversight of the study will be by the Steering Group which is multidisciplinary and have wide regional representation. There will in addition be a smaller executive group for day to day management. It is expected that most of this work will be done as a 'virtual group' by email. A writing and data analysis group will also be convened. Oversight of the study will be by the MARECA Steering Group which will have wide representation from surgeons, oncologists, trainees, pathologists, research nurses, the professional societies, patient representatives and those with experience of study management and statistics.

- 67. Harms, W., et al., *Current Treatment of Isolated Locoregional Breast Cancer Recurrences.* Breast Care (Basel), 2015. **10**(4): p. 265-71.
- 68. Aebi, S., et al., *Chemotherapy for isolated locoregional recurrence of breast cancer (CALOR): a randomised trial.* Lancet Oncol, 2014. **15**(2): p. 156-63.
- 69. https://www.ncri.org.uk/lwbc/.

15. Appendix

MARECA study flowchart

MARECA study National Practice Questionnaire on management of breast cancer locoregional recurrence

Management of breast cancer patients who present with locoregional recurrence was highlighted as a key research priority at the Association of Breast Surgery Gap Analysis meeting in 2019. Breast cancer locoregional recurrence is defined as breast cancer recurrence (invasive or DCIS) within the conserved breast, the ipsilateral skin or chest wall following mastectomy, or in the ipsilateral regional lymph nodes (axilla, supra- or infraclavicular, or internal mammary nodes). Currently there is no UK specific guideline on how these patients should be managed.

This questionnaire will aim to evaluate how UK breast units are managing patients with LRR. This will be followed by the MARECA study- National Study of Management of Breast Cancer Locoregional Recurrence and Oncological Outcome. This is a prospective observational multicentre cohort study which will describe the current management and prognosis of patients diagnosed with breast cancer locoregional recurrence in the UK.

We would like you to answer the National Practice Questionnaire within your entire MDT

team (maybe before or after the MDT meeting when all team members are present). The questionnaire will take approximately 20 minutes to complete and consists of questions about the number of cases your unit deals with followed by some scenario based questions designed to capture data on practice variation and areas of uncertainty.

Basic Unit information

-Please state the name of the participating hospital

-Please state the name, email address, and job title of the person entering data for your unit's questionnaire

-Does your unit treat patients referred from the breast screening programme?

Yes/No

-How many new breast cancers (invasive cancer and DCIS) do you manage per calendar year?

-Does your unit keep a prospective database of patients diagnosed with breast cancer LRR?

Yes/No

-Does your trust submit data on breast cancer recurrence to a national database?

Yes/No (If Yes, what data collection system is used? e.g. COSD)

-As an estimate, how many patients with LRR (without distant metastasis) do you manage at your unit per year?

- Less than 5 patients per year
- 5 to 10 patients per year
- More than 10 patients per year

-As an estimate, how many patients with LRR (with distant metastasis) do you manage at your unit per year?

- Less than 5 patients per year
- 5 to 10 patients per year

More than 10 patients per year

Practice Questionnaire Scenarios

MDT attendance for the National Practice Questionnaire

-Please state the presence and number of participating MDT members;

- Consultant Breast Surgeon (Yes/No; state number present)
- Consultant Oncologist (Yes/No; state number present)
- Consultant Histopathologist (Yes/No; state number present)
- Consultant Radiologist (Yes/No; state number present)
- Breast surgery trainees (Yes/No; state number present)
- Oncology trainees (Yes/No: state number present)
- Breast Care Nurses (Yes/No; state number present)
- Other MDT members (please state role and state number present)

Scenario 1. Diagnosis and staging investigations

-A 50 years old patient presents with a 3cm invasive recurrence in the ipsilateral breast after previous breast conserving surgery (BCS) and sentinel lymph node biopsy (SLNB) 3 years ago. The recurrence is in the same quadrant and has the same molecular receptor status as the original cancer. The tumour does not involve the skin or chest wall. Does your unit perform an axillary ultrasound scan (USS)?

Always/Usually/Occasionally/Never

-If this patient had previous axillary node clearance (ANC) instead of SLNB, does your unit perform an axillary USS?

Always/Usually/Occasionally/Never

-Would your unit offer staging investigations for this patient?

Always/Usually/Occasionally/Never

If yes, which staging investigations would be recommended (please tick all that apply)?

- CT chest/abdomen/pelvis
- Blood tests (e.g. FBC, U+E, LFTs, Ca, CA15-3)
- Isotope bone scan
- PET CT
- Others (please specify)

-If this patient had instead presented with an invasive recurrence in a different breast quadrant with a different molecular receptor status as the original cancer, would your unit offer staging investigations?

Always/Usually/Occasionally/Never

If this patient was found to have concurrent distant metastasis, would your MDT offer resection of the in-breast recurrence?

Always/Usually/Occasionally/Never

Scenario 2. Surgery to the breast

-A 76 year old patient underwent BCS and SLNB 10 years ago, followed by whole breast radiotherapy (WBRT). The previous histology had shown a 10mm area of grade 2 invasive ductal carcinoma (IDC) which was ER strongly positive and Her-2 negative. She had 3 nodes removed at SLNB of which none were positive. She had 5 years of letrozole treatment after surgery.

She now presents with a 1cm recurrent grade 1 ER+HER2- IDC 3 cm away from the primary scar. She wears a DD cup bra size and has good symmetry. She is fit and well. Would your MDT offer repeat BCS for this patient?

Always/Usually/Occasionally/Never

-If this patient had not received previous WBRT (she was PRIME 2 compliant), would your MDT offer repeat BCS?

Always/Usually/Occasionally/Never

-If your MDT offers repeat BCS for patients who had previously been treated with BCS and radiotherapy, does your MDT offer repeat breast radiotherapy?

Always/Usually/Occasionally/Never

Scenario 3. Axillary Management

-A 40 year old patient underwent BCS and SLNB for a 2.5cm grade 3 ductal cancer 3 years ago in the upper outer quadrant. Disease was resected with a clear margin and none of 2 lymph nodes contained any cancer. The disease was ER+ and Her2 negative. She had post-operative WBRT plus boost, chemotherapy, and 5 years of tamoxifen.

She now presents with an in-breast invasive local recurrence close to the primary scar measuring 10mm. Her pre-operative axillary assessment is benign clinically and on ultrasound. Staging is clear. What is your MDT's preferred mode of axillary management?

- Axillary Node Sampling (ANS: 4 node sample)
- Axillary Node Clearance (ANC)
- No axillary surgery
- Repeat SLNB without lymphoscintigram
- Repeat SLNB plus pre-operative lymphoscintigraphy
- Other (please specify)

-If this patient undergoes repeat SLNB and no SLN can be identified using your unit's standard tracer technique, how do you proceed?

- No further axillary dissection
- ANS
- ANC
- Other (please specify)

Scenario 4. Adjuvant treatment and patient follow up

-A fit and well 65 year old patient was treated with mastectomy and SLNB for a grade 3 node negative ER+HER2- 3cm IDC 7 years ago. She received adjuvant chemotherapy (3 cycles of anthracycline + cyclophosphamide, then 3 cycles of taxane) due to high Oncotype Dx score and completed 5 years of endocrine therapy. She did not require post mastectomy radiotherapy.

She now presents with a 1.5cm mastectomy skin flap invasive recurrence which is mobile. Staging is clear and she undergoes wide local excision of the skin flap and axillary surgery. Her resection margins are clear with negative lymph nodes. If this recurrent cancer was a grade 2 ER+HER2- IDC, would your MDT recommend adjuvant chemotherapy for this patient?

Always/Usually/Occasionally/Never

-If your unit offers Ki-67 testing, does your unit perform Ki-67 testing on the recurrent cancer in order to inform adjuvant chemotherapy decision-making for this patient?

Always/Usually/Occasionally/Never (Ki-67 test only utilised for primary breast cancer)/Not applicable as Ki-67 test not routinely offered at the unit

-Would your MDT recommend radiotherapy to the chest wall for this patient?

Always/Usually/Occasionally/Never

-For this scenario, if the patient had instead developed the ER+HER2- local recurrence 3 years after her primary breast cancer surgery (i.e. whilst still on adjuvant endocrine therapy), what adjuvant treatment(s) would your MDT recommend?

- Continue with current endocrine therapy + consider chemotherapy
- Continue with current endocrine therapy + no chemotherapy
- Switch endocrine therapy + consider chemotherapy
- Switch endocrine therapy + no chemotherapy
- No further endocrine therapy + consider chemotherapy
- No further endocrine therapy + no chemotherapy
- Other (please specify)

-For this scenario, if at the time of the recurrent cancer (ER+HER2- IDC) resection, she was instead found to have 1/3 macrometastasis in her axillary lymph node, would your MDT recommend adjuvant chemotherapy for this patient?

Always/Usually/Occasionally/Never

-For this scenario, if the patient had instead developed a recurrent cancer which was grade 3 triple negative IDC (and node negative), would your MDT recommend adjuvant chemotherapy for this patient?

Always/Usually/Occasionally/Never

Patient follow up policy

-Are patients in your unit followed up in the clinic after treatment for breast cancer LRR?

- No routine follow up
- Surgical clinic
- Oncology clinic

- Both surgical and oncology clinic follow up
- Other (please specify)

-What is the total duration of clinic follow up for these patients?

- 1 year
- 2 years
- 3 years
- 4 years
- 5 years
- No follow up protocol with individualised follow up
- Other (please specify)

Thank you very much for taking time to complete the survey. We are in the process of setting up a national study of **ma**nagement of breast cancer locoregional **re**currence and oncologi**ca**l outcome (the MARECA study). We welcome participation from all UK breast units. Please email the study team ([contact]) to register your interest. We especially welcome participation from trainees.

MARECA study Gantt chart

021	2022	2023	2024	2025	2026	2027	2028	2029	203
			_				_		
MARECA study national practice questionnaire Opened Feb 2021 with 41/60 study centres already completing the survey. Due to complete data return for all units by Aug 2021.	MARECA study national prospective cohort study 60 UK study centres to recruit patients newly diagnosed with breast cancer locoregional recurrence +/- distant metastasis for 24 months. Target recruitment of 500 patients. 330 patients required to determine the study's primary endpoint.			Determination of oncological outcome for the study cohort Study centres to return oncological outcome data at 3 and 5 year follow up.				222 C	
Study submitted for ethics application via IRAS: LTHT study sponsor.	NIHR portfolio adoption and study set up	Data validation and collation for analysis	Oncological outcome data collation and analysis		to / c	Collation of tissue/slide conse to design translational sub-stu / develop national guidelines with ABS		ub-stud	
Nati	ication 1: onal practice tionnaire results	Publication 2: Study Protocol	Results			l outcome o rt / identific	outcome of the / identification

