1.5.4 Adjuvant therapy options

Cancer recurrence may be due to survival and proliferation of clones that are resistant to a range of adjuvant therapies. Therefore, it would be of interest to examine the choice of endocrine and/or chemotherapy in patients with LRR. The CALOR trial demonstrated that patients with ER- (but not ER+) locally recurrent cancer benefited from further chemotherapy[57]. This randomised control trial demonstrated improved 5 year disease free survival (69% versus 57%) and overall survival (88% versus 76%) for patients who received chemotherapy after LRR resection surgery. There is also an increasing role for partial breast radiotherapy in patients treated with repeat BCS who have had previous BCS and radiotherapy[58]. Compared to treatment for primary breast cancer, there is a relative lack of clinical trial data on the efficacy of further adjuvant systemic therapy in patients diagnosed with LRR. The MARECA study will gather data on the type of adjuvant treatments currently used to treat patients diagnosed with LRR in the UK.

Given the complexity mentioned so far in the multidisciplinary management of patients with LRR, there is a need to examine long term oncological outcome and determine optimal patient management. The current literature reporting survival outcome for patients diagnosed with LRR are mostly based on single institution retrospective studies with

significantly different reported patient outcomes; a 5 year disease free survival (DFS) rate of 48 to 67% has been reported, and an equivalent overall survival (OS) rate of 61 to 82% has been reported[59]. Furthermore, these published studies are over 10 years old, reflecting the need to perform a prospective study to determine patient outcome, which reflects modern breast cancer treatment.

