4.1 National practice questionnaire

The MARECA study National Practice Questionnaire (NPQ) will consist of scenario-based questions (see Appendix) for the breast cancer multidisciplinary teams (MDTs) at the participating centres. It aims to document the current stated practice of breast cancer LRR management, and is designed to capture data on practice variations and areas of uncertainty in patient management. A trainee lead (specialty training registrar or specialty doctor) at each centre will be identified (via MFAC and BCTRCG) who will be asked to complete the questionnaire at the weekly breast MDT meeting and hence ensuring maximal input from all MDT members. The trainee lead will document the number of participants present at the MDT meeting, as well as the MDT composition (e.g. breast surgeons, oncologists, histopathologists, and radiologists). Trainee led research collaboratives have been successful in gaining high response rates for such national practice questionnaires (e.g. iBRA study[62]). The NPQ will be available online (www.surveymonkey.com) to enable ease of completion by each MDT and will be compatible with the current remote pattern of MDT meeting function (as a result of the coronavirus pandemic).

The NPQ will be completed by the participating sites between February and August 2021 prior to the commencement of the prospective cohort study. It has been developed to explore each MDT approach on the following themes;

- Pre-operative investigations.
- The type of breast and axillary surgery offered based on common clinical scenarios.
- Potential factors influencing the decision to offer repeat BCS.
- The type of systemic therapy and radiotherapy offered to treat LRR.

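### The Scenario 2 re-irradiation item has no 'Not applicable' answer, so MDTs that do not offer repeat BCS can be recorded as 'Never' re-irradiating

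*Protocol*

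**What the plan says.** Protocol section 4.1 says that the questionnaire "is designed to capture data on practice variations and areas of uncertainty in patient management", and Objective 1 in section 2.3 relies on it for stated MDT practice and geographical variation.

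In section 15, Scenario 2 first asks whether the MDT would offer repeat BCS to one previously irradiated patient, and then whether it would do so had she not been irradiated. The third item asks: "If your MDT offers repeat BCS for patients who had previously been treated with BCS and radiotherapy, does your MDT offer repeat breast radiotherapy". Its answers are "Always/Usually/Occasionally/Never", with nothing for an MDT to which the condition does not apply.

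Scenario 4 has a similar conditional item on Ki-67 testing. It explains in brackets what 'Never' means and adds a separate answer: "Not applicable as Ki-67 test not routinely offered at the unit".

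**The concern.** The stem restricts the question to MDTs that offer repeat BCS after radiotherapy, but the answer list does not. An MDT outside that group has no fitting answer. 'Never' is the nearest, and it is literally true of that MDT.

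A recorded 'Never' can then mean either of two practices: repeat BCS without further radiotherapy, or no repeat BCS after radiotherapy at all. A survey meant to describe variation should keep these apart. If they are pooled, the published share of MDTs that never re-irradiate after repeat BCS may be too high, and differences between regions in offering repeat BCS could appear as differences in radiotherapy practice.

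**Working it through.** The plan gives no figure to reproduce here. The check is a reading of the questionnaire items against each other, followed by the direction of any bias.

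**1. Does another item supply the answer?** The only other radiotherapy item is in Scenario 4: "Would your MDT recommend radiotherapy to the chest wall for this patient". Of that patient the scenario says: "She did not require post mastectomy radiotherapy". It therefore concerns first radiotherapy to the chest wall, and the Scenario 2 item is the only one on re-irradiation.

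**2. Can the first Scenario 2 item act as a filter?** That case is herself previously irradiated. An MDT that offers repeat BCS to no irradiated patient should therefore answer 'Never' to her.

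| MDT practice | Repeat BCS, irradiated case | Re-irradiation item | Effect of dropping 'Never' in column 2 |
|---|---|---|---|
| Offers repeat BCS, including this case | Not 'Never' | A valid answer | Kept, correctly |
| Offers no repeat BCS after radiotherapy | 'Never' | 'Never', or blank | Removed, correctly |
| Offers it to some irradiated patients, not this one | 'Never' | A valid answer | Removed, though valid |

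The third row is the cost of the filter. It should be uncommon. The case is a 1 cm recurrence 10 years after the first operation, and section 1.5.1 describes a small recurrent tumour after a longer interval as the profile most suitable for repeat BCS.

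**3. Direction and size.** Let f be the share of MDTs that do not offer repeat BCS after radiotherapy, t the share of those that tick 'Never' rather than leave the item blank, and q the true share never re-irradiating among MDTs that do offer it. Assume that all offering MDTs answer. Then

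- recorded share 'Never' = [f·t + (1 − f)·q] / [f·t + (1 − f)]
- excess over q = f·t·(1 − q) / [f·t + (1 − f)]

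The excess is zero if f = 0, t = 0 or q = 1, and is otherwise positive. The documents give none of f, t and q, so only the direction can be stated.

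**The case against.** The strongest reply is that the survey already carries its own filter. The Ki-67 item needs a 'Not applicable' answer because no earlier item asks whether the unit offers the test, whereas Scenario 2 asks about repeat BCS after radiotherapy first. Cross-tabulating two adjacent answers is an ordinary analysis step. An MDT outside the condition may also leave the item blank, and the online form may have had routing that the appendix does not show. All of this limits the harm. It does not remove the ambiguity in the printed item, and the protocol states no restriction of the denominator.

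Two stronger readings are tempting and are not supported.

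- **A numerical bias.** A reader might assume that 40% of offering MDTs never re-irradiate and that 10% to 50% of all MDTs do not offer repeat BCS and tick 'Never'. With t = 1 the formula gives 0.10 + 0.90 × 0.40 = 46% and 0.50 + 0.50 × 0.40 = 70%, an excess of 6 to 30 points. Neither input is in the documents, and the sum supposes that every non-offering MDT ticks 'Never' and that nobody applies the filter. It should not be quoted as the size of the problem.
- **An unmeasured theme.** A reader might infer that the survey fails a stated theme, because section 4.1 lists "The type of systemic therapy and radiotherapy offered to treat LRR" and neither radiotherapy item asks the type. The phrase can equally mean the type of systemic therapy, together with whatever radiotherapy is offered; on that reading the two frequency items address it. Nor is a comparison with the regimen recorded in section 5, item 3.41, a planned analysis.

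**Conclusion.** The point holds as a minor one. On the printed form, MDTs that do not offer repeat BCS after radiotherapy can be recorded as 'Never' re-irradiating, and the share never re-irradiating after repeat BCS may be overstated by an amount that cannot be computed from the documents. This assumes that some such MDTs exist, that at least some of them ticked 'Never', and that no unseen routing kept them from the item.

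Separately, partial versus whole breast radiotherapy was not asked in the survey. That is worth stating as a limitation, since section 1.5.4 says "There is also an increasing role for partial breast radiotherapy in patients treated with repeat BCS", but it is not a departure from the plan.

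The effect is confined to one result under Objective 1. The primary endpoint, the sample size and the cohort analysis are untouched.

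**What to change.** **Questionnaires already returned.**
- Report the re-irradiation item only among MDTs that did not answer 'Never' to repeat BCS in the irradiated Scenario 2 case.
- Show the cross-tabulation of the two items, with blanks as their own category.
- Give the unrestricted result as a sensitivity check, because the filter may drop an MDT that declines only that case.
- State in the report that the survey did not distinguish partial from whole breast radiotherapy.

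This needs no new data: one denominator rule, one table and one sentence.

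**If the questionnaire is reissued.** Add the answer 'Not applicable (repeat BCS not offered after previous radiotherapy)'. Under section 4.1 the survey was to run from February to August 2021, and the Gantt chart shows 41 of 60 centres already done. Protocol version 4.0 is dated 25/05/2022, so rewording cannot help answers already collected.
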